FACT-Lym Functional Assessment of Cancer Therapy - Lymphoma

FDA Food and Drug Administration

FDG fluorodeoxyglucose

FLT3 FMS-like tyrosine kinase-3

G-CSF granulocyte colony-stimulating factor

GCP Good Clinical Practice
GFR glomerular filtration rate

GI gastrointestinal

GM-CSF granulocyte macrophage colony

GVHD graft-versus-host disease

HBsAb hepatitis B surface antibody HBsAg hepatitis B surface antigen

HBV hepatitis B virus HCV hepatitis C virus

hCG human chorionic gonadotropin

HDC high-dose chemotherapy
HDL high-density lipoprotein

 $Itacitinib + everolimus \ in \ HL$

Version 11.0 Page 8 of 72

HDT high-dose chemotherapy

HIPAA Health Insurance Portability and Accountability Act of 1996

HIV human immunodeficiency virus

HL Hodgkin lymphoma

HMG 3-hydroxy-3-methyl-glutaryl

HR heart rate

HRQOL Health-Related Quality of Life During Therapy

HRS Hodgkin Reed-Sternberg

IB Investigator's Brochure

ICF informed consent form

ICH International Conference on Harmonization

IEC Independent Ethics Committee

IHC immunohistochemistry

IL interleukin

ILD interstitial lung disease

IN Investigator Notification

INCB039110 Itacitinib

INR international normalized ratio
IPI International Prognostic Index

IR immediate-release

IRB Institutional Review Board

ITT intent to treat

IVRS Interactive Voice Response System

IV intravenous

HDAC Histone deacetylases

JAK Janus kinase

LDH lactate dehydrogenase

LDi longest transverse diameter of lesion

LDL low-density lipoprotein

LFT liver function test

MedDRA Medical Dictionary for Regulatory Activities

Itacitinib + everolimus in HL

Version 11.0 Page 9 of 72

MF myelofibrosis

MPN myeloproliferative neoplasm
MRI magnetic resonance imaging

MTD maximum tolerated dose

mTOR mammalian target of rapamycin

MYD88 myeloid differentiation primary response 88

N/A not applicable

N/D not done

NCI National Cancer Institute

NCCN National Comprehensive Cancer Network

NCT National Clinical Trial
NHL non-Hodgkin lymphoma

NF-κB nuclear factor kappa light chain enhancer of activated B cells

NOAEL no-observed-adverse-effect-level

ORR objective response rate

OS overall survival

PCR polymerase chain reaction PCP Pneumocystis pneumonia

PD progressive disease

PET positron emission tomography

PET/CT positron emission tomography/computed tomography

PFS progression free survival

Pg prostaglandin
PgP P-glycoprotein

PHI protected health information

PI3K Phosphatidylinositol-4,5-bisphosphate 3-kinase

PI3Kδ PI3K delta isoform

PI principal investigator

PK pharmacokinetics

PI3K Phosphatidylinositol 3-kinase

PO by mouth

$Itacitinib + everolimus \ in \ HL$

Version 11.0 Page 10 of 72

PR partial response

QD once daily

QOL quality of life

R rituximab

RA rheumatoid arthritis

RP2D recommended Phase II dose

RT radiation therapy

SAE serious adverse event

SCT stem cell transplant

SOCS1 suppressor of cytokine signaling 1

SD stable disease

SMC Safety Monitoring Committee

SR sustained release

STAT signal transducer and activator of transcription

SUSAR Suspected unexpected serious adverse reaction

T temperature

TEAE treatment emergent adverse event

TME tumor microenvironment

TYK tyrosine kinase

ULN upper limit of normal

UPENN University of Pennsylvania

WBC white blood cell

WT weight

Version 11.0 Page 11 of 72

STUDY SUMMARY

Title Short Title Trial Phase IRB Number	AN OPEN-LABEL PHASE I/II SAFETY AND EFFICACY STUDY OF ITACITINIB IN COMBINATION WITH EVEROLIMUS IN SUBJECTS WITH RELAPSED/REFRACTORY CLASSICAL HODGKIN LYMPHOMA Itacitinib + everolimus in HL Phase I/II 831774		
Protocol Number	UPCC #: 45418; NCT03697408		
Study Population	Subjects with relapsed/refractory classical Hodgkin lymphoma (cHL)		
Rationale	While the majority of patients with classical Hodgkin lymphoma are cured, it is estimated that each year about 1000 patients will die from this disease in the United States alone. Therefore, new treatment strategies need to be developed for these patients.		
The molecular mechanisms underlying pathogenesis of malignant Ho and Reed–Sternberg (HRS) cells are complex. It has been demonstrathat Akt, a substrate of PI3-kinase, is constitutively activated in HL-d cell lines. Downstream effectors of Akt signaling include mTOR subwhich are also phosphorylated in HRS. Inhibitors of PI3-kinases and mTOR are clinically active in cHL as monotherapies. In a phase II trapatients with relapsed/refractory cHL, everolimus therapy was well tolerated and resulted in response rates of about 40%, but low complete remission rate of only 5%. Everolimus is currently part of the NCCN guidelines for treatment of cHL in relapsed/refractory setting.			
Another pathway which is activated in HRS includes the JAK/STAT pathway which promotes tumor cell proliferation and survival. JAK inhibitor produced modest responses in patients with cHL as monother			
	There is a rationale to combining mTOR inhibitor and JAK inhibitor in patients with cHL. In pre-clinical studies, co-treatment of mTOR inhibitor with JAK inhibitor resulted in synergistic activity against the proliferation of JAK mutated cell lines. Clinically, a study in various lymphoma subtypes using double inhibition of JAK and PI3-kinase pathway showed particular activity in cHL with ORR 60% and CR rate 20%. However, the combination was associated with pulmonary and liver toxicities and the study is currently on hold. These toxicities were attributed to the PI3-kinase inhibitor as a class.		

Page 12 of 72

	In our clinical trial, we plan to combine two oral agents which will target two pathways which are activated in HRS. We will administer concurrently itacinib (JAK inhibitor) with everolimus (mTOR inhibitor and a downstream effector of PI3-kinase) and hope to achieve synergistic effect without the severe toxicities observed in the PI3-kinase combination.		
This is an open-label, single-group, Phase I/II study of itacitinib in combination with everolimus in subjects with relapsed or refractory of Phase I will evaluate the safety and tolerability of itacitinib when comwith everolimus in subjects with relapsed refractory cHL using a stantage of the safety and tolerability of itacitinib when comwith everolimus in subjects with relapsed refractory cHL using a stantage of the safety of the combination in subjects with cHL at the dose determined in Phase I using a Simon 2-stage optic design. Subjects may continue to receive study treatment for a durating 2 years (24 cycles, each cycle consisting of 28 days) or until evidence disease progression, unacceptable toxicity, inability to commercially everolimus or consent withdrawal. Additional cycles of investigation treatment may be added if in the opinion of the investigator that the brisk ratio for the subject continues to be favorable.			
Methodology	Single Center, Open-Label, Prospective Phase I/II Clinical Trial		
Study Duration	Estimated duration of active enrollment is 3 years. The duration of the entire study can be up to 7 years, which would include 2 years of follow-up after the last patient completes end of treatment visit.		
Objectives	PHASE I		
	Primary Objective		
	To evaluate dose-limiting toxicities (DLTs) of combination treatment with itacitinib and everolimus occurring up to and during Day 28 of Cycle 1, and to establish a recommended Phase II dose (RP2D) in subjects with relapsed or refractory cHL.		
	Secondary Objective		
	To evaluate efficacy of itacitinib in combination with everolimus in terms of ORR, CR, PR, SD, duration of response, PFS, OS.		
	Exploratory Objective		
	To evaluate impact of itacitinib in combination with everolimus on QOL.		
	PHASE II		
	Primary Objective		
	To evaluate the efficacy of itacitinib in combination with everolimus in subjects with relapsed or refractory cHL as demonstrated by CR rate.		

Page 13 of 72

	Secondary Objectives		
	To evaluate efficacy in terms of ORR, PR, SD, duration of response, PFS, OS.		
Т	To evaluate the safety and tolerability of the treatment combination.		
	•		
	To evaluate impact of itacitinib in combination with everolimus on QOL.		
NT 1 C	•		
and Exclusion Criteria 2.3.4.	Up to 28 patients will be enrolled for planned 23 evaluable subjects n MAIN INCLUSION CRITERIA:		

Itacitinib + everolimus in HL
Version 11.0
Page 14 of 72

Investigational Products	 Males who have female partners of childbearing potential must agree to use an effective contraceptive method during the study and for 6 months following the last dose of study drugs. Subject must have access to everolimus via insurance or self-pay. MAIN EXCLUSION CRITERIA: Unable to sign informed consent. Pregnant or breast-feeding females (lactating females must agree not to breast feed while taking the investigational agents). Any condition, including the presence of laboratory abnormalities, which places the subject at unacceptable risk if he/she were to participate in the study or confounds the ability to interpret data from the study. Bilirubin < 3 × ULN in the presence of liver metastases or presence of documented Gilbert's syndrome (unconjugated hyperbilirubinemia) Concurrent use of other anti-cancer agents or therapies during study treatment. Use of any other experimental drug or therapy within 28 days of initiating treatment with the investigational agents. Known scropositive for or active viral infection with human immunodeficiency virus (HIV), hepatitis C (HCV), or hepatitis B virus vaccine are eligible. Previous use of JAK1 inhibitor (itacitinib) or history of disease progression on everolimus. Has a history, within the last 12 months, of (non-infectious) pneumonitis requiring systemic steroids, or current pneumonitis. Itacitinib is a small molecule inhibitor of the JAK family of protein which is manufactured in 100 mg sustained release tablets and will be provided to the participants by Incyte free of charge. The starting dose of itacitinib in Phase I will be 300 mg QD or decreased to 200 mg QD depending on observed DLTs. The recommended Phase II dose identified during Phase I will be the starting dose in Phase II. Subjects may ha
	Everolimus will be administered at a dose of 5 mg QD (5 mg tablets) concurrently with itacitinib. This is an FDA approved product and part of NCCN guidelines for relapsed/refractory cHL. It will be obtained by the patient from commercial pharmacy.
Reference Therapy	None. This protocol will be given to subjects with unmet medical needs for which there are no effective therapies known at this time.

Itacitinib + everolimus in HL

Version 11.0 Page 15 of 72

Duration of administration

Up to 2 years (24 cycles; each cycle is 28 days) of active therapy. Additional cycles of investigational treatment may be added if in the opinion of the investigator that the benefit risk ratio for the subject continues to be favorable. Subjects who discontinue study treatment will be followed for disease status, subsequent anticancer treatments, and survival for up to 2 years from completing end of treatment (EOT) visit. The study will end after the last subject completes 2 year follow-up or earlier once all subjects have discontinued study treatment, all subjects have died, have withdrawn consent, or are lost to follow-up.

Statistical Methodology

Sample size determination: Phase I portion of the study will utilize the standard 3 + 3 design with 6 to 15 patients enrolled. At least 6 patients will need to be treated at recommended phase 2 dose (RP2D) before proceeding to Phase II. A Simon optimal 2-stage design will be implemented to rule out the null CR rate of 5% against the alternative of 25% CR rate that might lead to larger, confirmatory studies. For 80% power and 5% alpha level, the first stage will enroll up to 9 evaluable subjects. If by week 16 there are no responders from the first 9 evaluable subjects with CR, the study will be stopped. Otherwise, additional subjects will be enrolled for a total of 8-17 evaluable treated at RP2D.

The study will be considered successful if 2 or more subjects achieve CR. Evaluable subject is defined as any subject who received at least 21 days of therapy and with at least one efficacy evaluation measured.

General data analysis plan: Descriptive statistics such as mean, standard deviation, median and range for continuous variable, and percentage for categorical variables will be computed. For the safety objective, all AEs will be listed and tabulated by organ system and in CTCAE preferred terms. Point estimate of the true AE rate and 90% exact confidence intervals will be computed. For the primary efficacy objective, a two-sided 90% confidence interval will be calculated for the CR rate as well as for the ORR. Duration of response, PFS, and OS will be summarized using Kaplan-Meier curve, and median survival time will be estimated with the associated 90% CI. FACT-Lym questionnaires will assess health related QOL.

Safety Evaluations

A DLT will be defined as the occurrence of any toxicities in Table 2 occurring up to and during Day 28 of Cycle 1, except those with a clear alternative explanation (e.g., disease progression) or transient (≤ 72 hours) abnormal laboratory values without associated clinically significant signs or symptoms based on investigator and sponsor determination. All DLTs will be assessed by the investigator using CTCAE v5 criteria (NCI 2018). In order to be included in the tolerability review, subjects must have received the cohort-specific dose of itacitinib and everolimus for at least 75% of the days during the 28-day surveillance period of Cycle 1 or have experienced a

Itacitinib + everolimus in HL
Version 11.0
Page 16 of 72

	DLT. Additional subjects may be enrolled to achieve a minimum cohort size should withdrawal or dose interruptions/reductions result in subjects being non-evaluable. The maximum tolerated DLT rate is set to be 30%. During Phase II portion of the study, a Bayesian stopping rule will be employed to monitor excess DLT rate. Under the assumption of a beta prior of (1,5), that is 1 DLT in 6 patients, the study will be stopped if 4 in 6, 5 in 9, 6 in 12, or 7 in 15 DLT are observed during cycle 1 in phase II of the study. The posterior probability that the true DLT rate is above 30% at each stopping would be around 77 to 79%.
	Subjects who experience a DLT or an unacceptable toxicity (i.e. not able to resume therapy within 28 days due to unresolved toxicity) beyond the DLT window will be also considered in the determination of the RP2D dose.
	Any grade 5 hematologic and non-hematologic event related to the study treatments (at any time) will be considered a DLT.
Data and Safety Monitoring Plan	This study will be monitored according to the Sponsor Data and Safety Monitoring Plan.

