4.5 Total Number of Subjects and Sites

The total planned number of evaluable subjects at UPenn will be 23 (including those in Phase I and II portions). To complete Phase I portion utilizing the 3 + 3 design, it is expected that 6 to 12 subjects will be enrolled. For phase II, 11 to 17 subjects will be enrolled. It is expected that total of 17-20 subjects will be treated at the RP2D dose since 3 to 6 patients from Phase I will be treated under the same regimen as Phase II patients. In order to be included in the tolerability review of Phase I, subjects must have received the cohort-specific dose of itacitinib and everolimus for at least 75% of the days during the first 28-day surveillance period or have experienced a DLT. Up to 5 additional subjects may be enrolled to achieve a minimum cohort size should withdrawal or dose interruptions/reductions result in subjects being non-evaluable during Phase I.

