7.2.2 Interim Safety Analyses

The safety analysis is based on Bayesian probability calculations and will be performed after the first 6 subjects treated at the RP2D and then after enrollment of 9, 12, and 15 subjects at RP2D dose. The max tolerated DLT (see section 3.2) rate is 30% and a beta prior of (1,5) is assumed (that is 1 DLT in 6 subjects). The study will be terminated if 4 DLTs in 6 subjects, 5 in 9, 6 in 12, or 7 in 15 are observed. The posterior probability that the true DLT rate is above 30% at each stopping would be around 77 to 79% (79%, 78%, 78%, and 77% respectively).

If there are two (2) study related deaths in the phase I portion, the study will be terminated.

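### The Bayesian toxicity rule has no boundary after 15 RP2D subjects although 17 to 20 are planned, and the text does not say to act when a boundary is already certain between looks

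*Combined protocol and SAP*

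**What the plan says.** The Study Summary (Safety Evaluations) lists four boundaries without a schedule: "the study will be stopped if 4 in 6, 5 in 9, 6 in 12, or 7 in 15 DLT are observed", counted in Cycle 1 of Phase II.

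Section 7.2.2 sets the model: "The max tolerated DLT (see section 3.2) rate is 30% and a beta prior of (1,5) is assumed". It schedules the analysis "after the first 6 subjects treated at the RP2D and then after enrollment of 9, 12, and 15 subjects at RP2D dose" and gives one boundary per look, with posterior probabilities of 79%, 78%, 78% and 77% that the true rate is above 30%. Section 8.7 repeats the looks and boundaries, but counts DLT-type events at any time, plus events that prevent restarting within 28 days. Neither section has a look after 15, and neither says what happens when a boundary count is reached before its look.

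Enrollment at the RP2D goes further. Section 7.1 needs 17 subjects there, and section 4.5 expects that a "total of 17-20 subjects will be treated at the RP2D dose". Section 3.1.3 counts six Phase I subjects toward Phase II. Under Table 1 a dose becomes the RP2D with at most 1 DLT in those six.

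**The concern.** A prespecified toxicity rule is meant to make stopping independent of discretion for as long as subjects enter. Here its last look falls 2 to 5 subjects before the planned end, so evidence as strong as the plan's own stopping standard could build up with no rule to act on it.

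The gap matters more because of the carry-over. With at most 1 DLT in the first six, the count at 9 is at most 1 + 3 = 4, below the boundary of 5. On Cycle 1 counts the looks at 6 and 9 therefore cannot trigger, which leaves only those at 12 and 15.

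A smaller matter is the interval between looks. If the next boundary has already been reached, the remaining subjects before the look cannot change the decision, yet the text is silent on whether to enroll them.

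**Working it through.** **Inputs.** Beta(1,5) prior, 30% limit, and boundaries 4/6, 5/9, 6/12 and 7/15 (7.2.2, 8.7). N = 17 (7.1) or up to 20 (4.5). At most 1 DLT in six carried over (3.1.2 Table 1, 3.1.3). True rates of 30% and 50% are assumptions for illustration. Each subject's event is counted in Cycle 1, in order of entry.

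**1. The plan's own figures.** P(rate > 0.30 | x of n) = 1 − F(0.30; 1 + x, 5 + n − x), where F is the Beta distribution function.

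- 4/6: 0.790; 5/9: 0.781; 6/12: 0.775; 7/15: 0.772. All four agree with the plan.

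**2. After 15.** An unstopped trial has at most 6/15 (0.608).

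- n = 16: at most 7/16 = 0.723, below every stated level.
- n = 17: 8/17 = 0.814.
- n = 19 and 20: 9/19 = 0.847; 9/20 = 0.811.

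The plan's step of one event per three subjects continues to 8/18 = 0.771, the same 77% standard when rounded.

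**3. Gain from 8 within 18, with at most 1/6 carried over, true rate 50%.** Given 0 or 1 event in six, the weights are 1/7 and 6/7. Count sequences among subjects 7 to 15 (2⁹ = 512):

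- Stopped under the present rule: from 1, 136/512; from 0, 47/512. Weighted: 6/7 × 0.2656 + 1/7 × 0.0918 = 0.241.
- Unstopped at 6/15: from 1, (126 − 6)/512; from 0, (84 − 1)/512. Weighted: 0.224. The subtracted sequences stop at 12.
- At 5/15: 126/512 = 0.246 from either start.
- Added stopping by 18: 0.224 × P(at least 2 of 3) + 0.246 × P(3 of 3) = 0.224 × 0.5 + 0.246 × 0.125 = 0.143. Total 0.384.
- If N = 17, only 6/15 followed by two events counts: 0.224 × 0.25 = 0.056. Total 0.297.

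The same recursion gives:

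| First six | True rate | Present rule | With 8 within 18, N ≥ 18 | N = 17 |
|---|---|---|---|---|
| at most 1/6 | 50% | 24.1% | 38.4% | 29.7% |
| at most 1/6 | 30% | 2.2% | 3.8% | 2.7% |
| all new | 50% | 74.9% | 81.3% | 77.6% |
| all new | 30% | 19.2% | 22.0% | 20.1% |

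**4. Adding 9 events at n = 19 or 20.** A trial still open at 18 has at most 7 events, so this needs 7/18 and then two events. At a true rate of 50% with at most 1/6 carried over, P(7/18) = 0.375 × (0.224 + 0.246) + 0.125 × 0.176 = 0.198, where 0.176 is P(4/15) = 6/7 × 84/512 + 1/7 × 126/512. The addition is 0.198 × 0.25 = 0.050, for a total of 43.3%. At a true rate of 30% the same step takes 3.8% to 4.3%, or 22.0% to 22.7% with all-new subjects.

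**5. Between looks.** The reachable states with the next boundary already certain are 4/4 (0.901), 4/5 (0.850), 5/8 (0.835), 6/11 (0.825) and 7/14 (0.818). The overrun is two subjects at 4/4 and one at each of the others. With at most 1/6 carried over, only 6/11 and 7/14 can occur. Acting at once leaves every stop decision unchanged. At a true rate of 50% and N = 17, expected N falls from 10.91 to 10.49 (all new) or from 16.23 to 16.15 (at most 1/6).

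**The case against.** Fixed-look Bayesian boundaries are an ordinary design choice, and the stated posteriors are right. That stands: this is a gap in coverage, not an arithmetic error.

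A reader might infer that the protocol orders enrollment to continue past a certain boundary. It does not. The point rests on silence in 7.2.2 and 8.7, and the Study Summary sentence can be read as stopping whenever a count is met.

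A reader might also cite 5/7, 6/10 or 7/13 as overrun states. On Cycle 1 counts they cannot occur: 5 in 7 requires at least 4 in 6, 6 in 10 at least 5 in 9, and 7 in 13 at least 6 in 12, so the previous look would already have stopped the trial. Late events counted under 8.7 could produce them, but that case is not modeled here. Nor does the gap bite for every subject after 15: at 16 no reachable count exceeds a stated level.

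If enrollment ends at 17, the eighth event arrives when accrual is complete, so the added boundary spares no one enrollment. This also stands. It then affects only the study's conclusion and the decision about subjects still on treatment.

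Finally, subjects are not without protection. Section 8.7 has rules for deaths, section 3.2 allows a lower RP2D after later toxicity, section 5.6 covers individual holds, and section 6.9.1 lets the sponsor terminate. A Sponsor Data and Safety Monitoring Plan exists but is not reproduced. None of these, as written in the protocol, is a toxicity-rate boundary after 15.

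**Conclusion.** The concern holds in two parts of unequal weight.

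The main part is the missing boundary after 15. From subject 17 the plan's own evidence standard can be exceeded with no toxicity-rate rule. In the carry-over setting that the protocol creates, one more boundary adds 14 percentage points of stopping probability at a true rate of 50% if 18 or more are enrolled, and 6 points if enrollment ends at 17.

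The second part, action between looks, is a clarification. It saves about 0.08 subject per trial with carry-over and 0.42 with all-new subjects, at a true rate of 50% and N = 17.

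These sizes assume Cycle 1 counting in order of entry and the stated true rates. The upper limit of 20 rests on section 4.5 alone. If only Phase II subjects count, as the Study Summary can be read, the uncovered subjects are the 16th and 17th. The documents do not support the stronger conclusion that the rule is miscalculated or that subjects are left without safety oversight.

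**What to change.** In the Study Summary, 7.2.2 and 8.7, state that the study stops as soon as the cumulative count reaches 4 within the first 6 RP2D subjects, 5 within 9, 6 within 12 or 7 within 15, without waiting for the look. Extend the same Beta(1,5)/30% rule to the last RP2D subject: 8 events within the first 18, and 9 events at n = 19 or 20. Use one counting basis in all three places, and report the operating characteristics with and without the carried-over Phase I subjects.

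The first change is wording only. The second raises stopping at a true rate of 30% by 1.6 points with carry-over or 2.8 points with all-new subjects (0.5 and 0.9 points if enrollment ends at 17). The boundary at 19 to 20 adds a further 0.5 to 0.8 points if 20 are enrolled. The protocol should state this increase.
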